7 STATISTICAL ANALYSIS

7.1 Determination of Sample Size

CCI [REDACTED]. In general, the maximum sample size in the dose-escalation stage will be determined by sponsor and investigator based on the accumulated safety data and the mTPI-2 design (Ji 2013). CCI [REDACTED].

Patients who withdraw from the study prior to completing the DLT assessment window for reasons other than DLT or receive less than 75% of assigned study medication during DLT assessment window will be replaced. This may result in the actual enrollment exceeding the planned enrollment.

CCI [REDACTED]

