 - The target probability of toxicity (p_T) is set to 30%.
 - Both epsilon 1 (ϵ_1) and epsilon 2 (ϵ_2) are set to 0.05.
- This stage will end when any of the following criteria is met:
 - The dose level 1 demonstrates an excessive toxicity, i.e., 3 DLTs are observed out of the first 3 patients at dose level 1.

- The maximum sample size is reached.
- The MTD and/or RP2D are confirmed.

The rules applied in the dose escalation stage are as follows:

- The starting dose is dose level 1: 5 mg QD.
- If a lower dose is needed upon results from dose level 1, dose level -1 will be explored.
- Three patients will be enrolled for the initial cohort (dose level 1).
- At the end of the DLT assessment window for a dose level, the decision on the dose of the next dose level will follow the rule specified in [Figure 1](#), which leads to enrollment of another 3 patients at the next step.
- In the event that the first two patients within a given dose level experience DLT events but the third patient has not yet begun protocol treatment, the third patient should receive a lower dose per the mTPI-2 algorithm.

At the end of Stage 1, the MTD will be determined based on the number of patients treated and the number of experienced DLTs at each dose level.

Stopping rules for individual patients in the dose escalation stage are located in Section [5.8.3.1](#). Stopping rules for dose cohorts or for the study in the dose escalation stage are available in Section [5.8.4.1](#).

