4.1.1.2 Definition of Dose Limiting Toxicity

Dose limiting toxicities are defined as the occurrence in the DLT assessment window of any of the following TEAEs, unless equivocally due to underlying malignancy or an extraneous cause:

- a. Non-hematologic toxicity: All non-hematologic TEAEs of Grade 3 or greater with the exception of:
 - i. Grade 3 nausea or vomiting that can be controlled by supportive therapy
- b. Hematologic toxicity:
 - i. Grade 4 neutropenia lasting for more than 5 days
 - ii. Grade 4 thrombocytopenia or Grade 3 thrombocytopenia with bleeding event or requiring platelet transfusion
 - iii. Grade ≥ 3 febrile neutropenia (defined as ANC $< 1000/\text{mm}^3$ with a single temperature $> 38.3^\circ\text{C}$ [101°F] or a sustained temperature of $\geq 38^\circ\text{C}$ [100.4°F] for more than 1 hour)
 - iv. Grade 4 anemia not explained by underlying disease
- c. Any TEAE requiring a dose delay of ≥ 15 days
- d. Any case of Hy's Law

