4.1.1.4 Definition of a DLT-Evaluable Patient

For decisions on dose escalation, each dose cohort shall present protocol-required number of DLT-evaluable patients. Any patient is DLT evaluable if he/she meets the following criteria:

A patient is DLT evaluable if he/she:

- has received at least 75% of the assigned dose of study treatment during the DLT assessment window (i.e., Days 1-28);
- or
- has not completed the DLT assessment period due to a DLT.

Patients who are not DLT evaluable in a dose cohort will be replaced to guarantee the protocol-required number of DLT-evaluable patients for each dose cohort.

4.1.1.5 Dosing Beyond Cycle 1

Patients who complete DLT assessment window and are deemed by the investigator to be benefiting from HMPL-689 treatment may continue with HMPL-689 treatment until disease progression, death, intolerable toxicity, at investigator's discretion that the patient can no longer benefit from the study treatment, withdrawal of consent, or the end of study, whichever occurs first. Conversely, if, in the opinion of the attending principal investigator, the patient may receive clinical benefit from a higher dose, then, at the request of the principal investigator and with the approval of the sponsor, the patient may be able to participate in intra-patient dose escalation (Section 4.1.1.1).

During the study treatment period, including the DLT assessment window, patients will not be allowed to make up missed doses.

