5.4.1 During Dose Limiting Toxicities Assessment Window

If a patient experiences a DLT, dosing of HMPL-689 will be interrupted and supportive therapy administered as required in accordance with local practice/guidelines. Refer to Section 6.8 for toxicity management recommendations.

Patients who experience a DLT may resume dosing at the same or previous lower dose level at the discretion of the treating physician given that the toxicity is resolved or improved to the baseline level. If a patient experiences an intolerable toxicity at the reduced dose level, he/she will be discontinued from the study treatment. Patient cannot be dose-reduced by more than 2 dose levels. Once reduced, the dose cannot be re-escalated.

No dose reduction in patients without DLT is permitted in the DLT assessment window without the sponsor's approval.

5.4.2 After Dose Limiting Toxicities Assessment Window of Stage 1 or at Stage 2

After DLT assessment window of Stage 1 or at Stage 2, the dose of HMPL-689 may be interrupted if any of the following is observed:

- Any grade pulmonary toxicity
- Any grade diarrhea/colitis
- Grade 3 or 4 hematologic toxicity
- Grade 3 or 4 non-hematologic toxicity (except for alopecia and skin eruption, nausea, vomiting, diarrhea or constipation if well-controlled by systemic or topical medication)

Refer to Section 6.8 for detailed toxicity management recommendations for potential class-related toxicities and dose modification of HMPL-689.

For all other toxicities, treatment with HMPL-689 should be withheld until the toxicity resolves to CTCAE Grade ≤ 2 . Dosing may then be resumed at either the same dose level or the previously evaluated lower dose level if the toxicity is improved to CTCAE Grade ≤ 2 within 2 weeks, per investigator's discretion. If treatment is resumed at the same dose, and the patient experiences the same toxicity of Grade 3 or 4, the dose should be reduced following resolution of the event. If the patient continues to experience intolerable toxicity, a second dose reduction to a previously evaluated lower dose is permitted.

In all cases, every patient is allowed to reduce HMPL-689 dose only twice. If a patient continues to experience intolerable toxicity after 2 dose reductions, or if dosing with HMPL-689 is interrupted for >14 consecutive days due to toxicity (except for those with additional guidance provided in Section 6.8), treatment should be discontinued, unless otherwise agreed by the investigator and the sponsor.

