7.3.2 Safety Analysis

Safety parameters, including study drug exposure, DLTs, recorded TEAEs, clinical laboratory parameters, vital signs, 12-lead ECG parameters and physical examination findings, will be summarized by dose level across different stages for the FAS.

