6.4. DLT EVALUABLE ANALYSIS SET (DEAS)

The DLT Evaluable Analysis Set (DEAS) is defined as all patients enrolled in the dose escalation phase of the study who are evaluable for DLT assessment. A subject is DLT evaluable if he/she meets the following criteria:

 has received at least 75% of the assigned dose of study medication during the DLT assessment window

OR

has not completed the DLT assessment period due to a DLT

DLT assessment window is defined as the treatment period of 28 days (i.e., from Cycle 1, Day 1 [the day of the first administration of treatment] through Cycle 1, Day 28).

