17. SAFETY OUTCOMES

All summary results for safety outcomes will be based on the FAS, except DLTs summaries which are based on the DEAS.

Adverse Events (AEs) will be coded using MedDRA version 26.0 or higher. AE and laboratory test results severity will be performed with the National Cancer Institute Common Terminology criteria for adverse events (NCI CTCAE) V5.0.

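### As worded, the DLT-evaluability and replacement rules can remove patients who had a DLT from the set on which the DLT rate is computed, biasing that rate downward

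*Protocol*

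**What the plan says.** Protocol 4.1.1.4 and 7.2 and SAP 6.4 give the same two routes to DLT-evaluability. The first is receipt of 75% or more of the assigned dose during the 28-day window. The second is that the patient "has not completed the DLT assessment period due to a DLT". Protocol 4.1.1.4 links this to decisions: "For decisions on dose escalation, each dose cohort shall present protocol-required number of DLT-evaluable patients". Patients who are not evaluable are replaced.

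Protocol 7.1, the synopsis and SAP 4.2 carry a separate replacement sentence. Its first branch, withdrawal before the end of the window, exempts withdrawals caused by a DLT. Its second branch does not: patients who "or receive less than 75% of assigned study medication during DLT assessment window will be replaced".

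On dosing, Protocol 5.4.1 interrupts treatment for a DLT and then states: "Patients who experience a DLT may resume dosing at the same or previous lower dose level at the discretion of the treating physician", provided the toxicity has resolved or improved to baseline. Missed doses are not made up (Protocol 4.1.1.5 and 5.2.4). Criterion (c) of the DLT definition (Protocol 4.1.1.2) is itself a dosing gap: "Any TEAE requiring a dose delay of" 15 days or more.

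On analysis, SAP 17 uses the FAS for safety, "except DLTs summaries which are based on the DEAS", and SAP 17.1 takes the DEAS as the denominator for DLT percentages. Protocol 7.3.2 includes DLTs among the safety parameters that "will be summarized by dose level across different stages for the FAS".

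**The concern.** A patient can have a DLT, be held, resume, reach Day 28 and still have received less than 75% of the dose. Nothing in either limb, read literally, keeps that patient in the DEAS. The patient drops out because of the outcome being measured and is replaced by someone who may have no DLT, so the error can only run toward a lower rate.

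The replacement sentence is a second, separate defect. However the second limb is read, its dose branch also calls for replacing patients who stopped because of a DLT, whom Protocol 4.1.1.4 counts as evaluable.

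Incidence of DLTs is a Stage 1 primary endpoint (Protocol Table 1, SAP Table 1), and SAP 17.1 computes it on the affected set. If the same counts entered Figure 1, escalation would also look safer than it was.

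**Working it through.** **1. The plan's own chart.** With a target of 30%, an equivalence interval of (25%, 35%), an assumed Beta(1,1) prior and an assumed exclusion cut-off of P(p > 0.30) > 0.95, 89 of the 90 cells of Figure 1 reproduce. The exception is 2 of 2: the chart prints D, and the calculation gives DU because P(p > 0.30) = 0.973. It disappears if exclusion applies only from three patients on. The cells used below are as printed: 0/3 E, 1/3 S, 1/4 S, 1/6 E, 2/7 S.

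**2. Can the gap be reached?** Dose fraction = (28 − days missed)/28, for once-daily dosing resumed at full dose.

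| Days missed | Fraction | 75% met? |
|---|---|---|
| 7 | 21/28 = 75.0% | yes |
| 8 | 20/28 = 71.4% | no |
| 14 | 14/28 = 50.0% | no |
| 15 | 13/28 = 46.4% | no |

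An 8-day hold allows a dose by Day 28 if it starts by Day 20; a 14-day hold, if it starts by Day 14. Protocol 5.8.3.1 stops dosing when a DLT has not returned to Grade 1 or lower within 14 days, so the clearest case is a hold of 8 to 14 days followed by resumption.

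**3. Criterion (c).** A hold from Day s through Day 28 misses 29 − s days. For s = 21 that is 8 days (71.4% received); for s = 14 it is 15 days (46.4%). A delay of 15 days or more therefore leaves at most 71.4% whenever it starts by Day 21, and at most 46.4% if it starts by Day 14. The dose branch of the replacement sentence captures all of these DLT patients.

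**4. Direction.** Removing one DLT patient changes x/n to (x − 1)/(n − 1), which is smaller whenever x < n. Only if every treated patient had a DLT can the observed rate stay the same.

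**5. Expected size.** Let p be the true DLT probability and f the share of DLT patients excluded (assumed). A fraction pf of treated patients is lost, so the expected DEAS rate = p(1 − f)/(1 − pf). At p = 0.30 and f = 0.25: 0.225/0.925 = 24.3%. A simulation of this case with six evaluable patients gave 0.2435 against 0.2432 from the formula.

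If escalation used evaluable patients only, let r be the expected DEAS rate. With cohorts of three, the chart escalates by six patients after 0/3, or after 1/3 followed by 0/3. The probability is (1 − r)³ + 3r(1 − r)² × (1 − r)³. At f = 0: 0.343 + 0.441 × 0.343 = 49.4%.

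| f | Expected DEAS rate at p = 30% | Chance of escalating by n = 6 |
|---|---|---|
| 0 | 30.0% | 49.4% |
| 5% | 28.9% | 51.6% |
| 10% | 27.8% | 53.9% |
| 25% | 24.3% | 61.4% |
| 50% | 17.6% | 75.9% |

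**6. One patient in one cohort**, replaced by a patient without a DLT:
- Cohort of three: 1/4 = 25% of all treated (S), but 0/3 = 0% in the DEAS (E).
- Cohort of six: 2/7 = 28.6% of all treated (S), but 1/6 = 16.7% in the DEAS (E).

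**The case against.** The strongest reply concerns the second limb. SAP 6.4 describes the window as a period of treatment, so a patient taken off drug for a DLT can be said not to have completed it and would stay in the DEAS. That reading is reasonable, but it is not written. Protocol 5.8.4 separates stopping drug from leaving the study, and a patient who resumes and reaches Day 28 is hard to describe as not having completed the period.

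Second, replacement is not exclusion. The sample-size sentence governs enrolment; the DEAS definition governs the table. This stands: for a patient who left the window because of a DLT, replacement contradicts 4.1.1.4 without removing the DLT. Exclusion comes only through the two limbs.

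Third, the effect on dose selection is limited. Protocol 4.1.1 says "the MTD will be determined based on the number of patients treated and the number of experienced DLTs at each dose level", and under Protocol 5.8.4.1 the SRC reviews all available data. That also stands, which is why no wrong MTD is claimed. It still sits awkwardly with 4.1.1.4, which ties escalation to evaluable patients.

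Fourth, DLTs are listed, the AE listing flags them, and SAP 9.1 provides a listing of who is in each analysis set. An excluded patient could be found by cross-checking, but the listings do not correct the percentage.

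Finally, f is unknown, and at 5% or 10% the expected rate stays inside (25%, 35%). True, but with cohorts this small a single patient matters more than the average.

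**Conclusion.** The concern holds as a conditional one. Read literally, the rules drop a patient who had a DLT, completed the window and received less than 75% of the dose, and the expected DEAS rate is then below the true rate. At a true 30% it is 28.9% to 17.6% for f from 5% to 50%. These figures rest on the assumed f and on the literal reading of the second limb. The documents report no such patient. The FAS/DEAS conflict and the missing DLT exception in the replacement sentence exist whether or not one occurred. With enrolment halted, what can still be put right is the reported Stage 1 DLT table.

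**What to change.** - In SAP 6.4, define a patient as DLT-evaluable if (a) any DLT occurred in Days 1 to 28, whatever dose was received, or (b) no DLT occurred and 75% or more of the assigned dose was received.
- In SAP 4.2, limit replacement to patients without a DLT.
- Align the synopsis (evaluability definition and sample-size sentence) and Protocol 4.1.1.4, 7.1 and 7.2.
- Choose one population for DLT summaries and state it in both Protocol 7.3.2 and SAP 17.
- Produce the Stage 1 DLT table on the corrected set, with a footnote identifying any DLT patient whom the present wording would have excluded, or stating that there were none.

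The cost is low: about seven wording changes and one population statement. DLTs are already collected on their own CRF page, so no new data are needed. The SAP changes alone correct the table; aligning the protocol needs an amendment. No dosing, interruption or resumption rule is altered.

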7.1.1 Stage 1: Dose Escalation Stage

The maximum sample size at mTPI2 for this stage will be determined by sponsor and investigator based on the accumulated safety data and mTPI-2 design (Ji 2013). The maximum sample size under the mTPI-2 method is $k \times (d + 1)$, where k denotes the cohort size and d denotes the number of doses. The minimum cohort size in this study is 3 patients per cohort. To ensure that the highest dose (if needed) is reached per the mTPI-2 design and the availability of additional cohorts, it is estimated that approximately CCI [REDACTED] patients will be needed in this study.

7.1.2 Stage 2: Dose Expansion Stage

CCI [REDACTED]

CCI

CCI

7.2 Analysis Populations

The following analysis populations are defined for the study:

Full Analysis Set (FAS):

The FAS is defined as all patients who receive at least one dose of HMPL-689. The FAS will be used for analysis of safety data and efficacy endpoint PFS.

DLT Evaluable Analysis Set: All patients enrolled in the dose escalation phase of the study who are evaluable for DLT assessment. A subject is DLT evaluable if he/she meets the following criteria:

- has received at least 75% of the assigned dose of study medication during the DLT assessment window

OR

- has not completed the DLT assessment period due to a DLT

Efficacy Analysis Set (EAS):

All patients who receive at least one dose of HMPL-689 and have a baseline tumor assessment and at least one post-baseline assessment will be considered evaluable for anti-tumor efficacy endpoints such as ORR, clinical benefit rate (CBR), TTR, and DoR.

Pharmacokinetics Analysis Set (PKAS):

The PKAS is defined as all patients who received at least one dose of HMPL-689 and have at least one PK sample obtained and analyzed.

7.3 Statistical Methods

Data will be summarized by dose level, subtype of malignancy and for overall as appropriate. Continuous assessments will be summarized by number of patients (n), mean, standard deviation, median, minimum and maximum. For categorical variables, descriptive statistics will include the number and percentage of patients for each category.

All statistical analysis will be performed under the direction of HUTCHMED Limited personnel. Details of the statistical analysis and data reporting will be provided in the Statistical Analysis Plan (SAP) document, which will be finalized prior to database lock.

The timing of analysis for each cohort may be different depending on completion of each cohort; final analysis of the study will be conducted at the time of the analysis of the last cohort.

7.3.1 Disposition of Patients Enrolled in the Study

The patient disposition in the dose escalation and dose expansion stages will be summarized for each dose level.

Study drug administration data will be listed by dose level. The total duration of exposure, dose intensity, and relative dose intensity of HMPL-689 will be summarized by descriptive statistics.

7.3.2 Safety Analysis

Safety parameters, including study drug exposure, DLTs, recorded TEAEs, clinical laboratory parameters, vital signs, 12-lead ECG parameters and physical examination findings, will be summarized by dose level across different stages for the FAS.

7.3.2.1 Dose Limiting Toxicities

All DLTs will be listed.

7.3.2.2 Adverse Events

All AEs will be coded using the Medical Dictionary for Regulatory Activities (MedDRA) and the corresponding intensity will be graded according to NCI CTCAE v.5.0. Analysis of AEs will be performed for TEAEs, which are defined as AEs that onset or worsen in severity on or after the first dose of HMPL-689. All TEAEs will be summarized in frequency and percentage of patients for each dose level.

The same analysis will be performed for SAEs, study drug-related TEAEs assessed by the investigators, TEAEs leading to dose adjustment, or treatment discontinuation, and AEs of special interest.

7.3.2.3 Clinical Laboratory Test Values

Descriptive statistics for each clinical laboratory test will be presented for each dose and scheduled visit. Laboratory test values from the hematology and chemistry panels, which are gradable in NCI CTCAE, will be summarized by the shift of NCI CTCAE grade from baseline to the worst grade on study treatment period.

Selected laboratory tests will be plotted over time for each patient. All laboratory test results will be listed.

7.3.2.4 Vital Signs

Vital signs (systolic and diastolic blood pressure, heart rate, respiration rate, and body temperature) will be summarized with descriptive statistics by dose level and visit.

Selected vital signs tests will be plotted over time for each patient. All vital sign data will be listed.

7.3.2.5 12-Lead ECGs

Descriptive statistics for ECG parameters (PR interval, QRS interval, RR interval, QT interval, QTcF interval [QT interval/cube root of RR interval], and heart rate) will be presented by dose level and visit. Refer to Section 7.3.5 for further details.

7.3.2.6 Physical Examination

All physical examination findings will be listed.

7.3.3 Pharmacokinetic Analysis

Pharmacokinetic parameters will be analyzed with the PKAS. A non-compartmental model analysis will be performed for plasma concentration data from the escalation stage using Phoenix WinNonlin. Individual and mean plasma concentration of HMPL-689 versus time data will be tabulated and presented. The individual and mean PK parameters determined following analysis of the concentration of HMPL-689 versus time data, will include, but are not limited to AUC, C_{max} , T_{max} , C_{min} , CL/F and AR. N, mean, standard deviation, minimum, median, maximum, geometric mean, and coefficient of variation [%CV] will be presented. The actual times of plasma sample collection will be used in the determination of the PK parameters. Individual and mean HMPL-689 concentrations will be plotted by dose level. Details of the PK analysis, including data handling rules and software used to perform the PK analysis, will be provided in the PK analysis plan (PKAP).

Plasma concentration data of HMPL-689 from the expansion stage will be tabulated and presented as described in the PKAP.

7.3.4 Efficacy Analysis

Efficacy endpoints will be summarized by dose level for each type of malignancy.

The best percent change from baseline (%) in the target lesion, ORR, CBR, and the corresponding 95% CI based on Clopper-Pearson method will be presented by dose level.

The PFS, TTR, and DoR will be summarized with Kaplan-Meier (KM) method if data permit, and the corresponding KM curve will be plotted.

ORR, CBR, PFS, TTR, and DoR data will be listed for all patients.

Tumor assessment in different types of malignancies will be evaluated according to specified guidelines/criteria:

- CLL: the modified International Workshop on CLL guideline ([Hallek 2008](#), [Cheson 2012](#)), see [Appendix 5](#).
- LPL/WM: consensus of international workshops on WM (IWWM-7 consensus) ([Dimopoulos 2014](#)), see [Appendix 6](#).
- Other lymphomas: Lugano Response Criteria for Hodgkin and NHL ([Cheson 2014](#)), see [Appendix 7](#).

In the evaluation of the tumor response endpoints (ORR, TTR, CBR, DoR, and PFS), the investigator-assessed data will be utilized for tumor assessment.

7.3.5 Pharmacodynamics (Electrocardiogram) Analysis

Patients who 1) receive at least 1 dose of study drug and 2) have baseline and at least 1 postdose ECG measurement will be evaluable for pharmacodynamic (ECG) evaluation. Patients who had reduced dosage, prolonged dose interruption of >2 days in cycle 1, any dose interruption within 3 days before Cycle 1 Day 15, or were discontinued from the study prior to the completion of ECG data collection (Cycle 1 Day 15) will be excluded. For each of the ECG parameters, the average values from the 3 readings of a triplicate ECG set will be used in the analysis.

For all ECG parameters, the baseline will be defined as the mean values of the triplicate ECG measurements taken at predose on Cycle 1 Day 1.

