2.3 Clinical Experience of HMPL-689

See the investigator's brochure (IB) for up-to-date clinical experience for HMPL-689.

Study CCI (Completed)

This was a phase 1, randomized, double-blind, placebo-controlled, first-in-human, single dose escalation study to investigate the safety, tolerability and PK of HMPL-689 in Australia (completed). The study enrolled 48 healthy volunteers who were randomized into HMPL-689 group or placebo group at a 3:1 ratio. Subjects received oral single doses of HMPL-689 or placebo in sequence at dose levels of 1, 2.5, 5.0, 10, 20, and 30 mg under fed condition.

Of 36 subjects in the HMPL-689 treatment group, 15 subjects (41.67%) experienced a total of 19 adverse events (AEs). Adverse events reported in at least one subject included upper respiratory tract infection (13.9%), headache (8.3%), dyspepsia (5.6%), oligospermia (5.6%), flatulence (2.8%), back pain (2.8%), musculoskeletal pain (2.8%), eczema (2.8%), skin burning sensation (2.8%), and eye irritation (2.8%). Adverse events that were assessed by the investigator as related to HMPL-689 were upper respiratory tract infection (8.3%), headache (5.6%), dyspepsia (5.6%), flatulence (2.8%), and back pain (2.8%). Alanine transaminase increase was noticed in 5.56% of subjects in the HMPL-689 group and 8.33% of subjects in the placebo group. Aspartate transaminase increase was noticed in 19.44% of subjects in the HMPL-689 group and 25% of

subjects in the placebo group; all of the ALT/AST increases were of Grade 1. No Grade ≥ 3 AE was reported. No dose limiting toxicity (DLT) was noted.

The single dose PK of HMPL-689 was evaluated in 36 healthy volunteers in the HMPL-689 treatment group under fed condition. HMPL-689 was absorbed after oral administration with a median T_{max} of 1.5 to 3 hours. The HMPL-689 exposures, as measured by C_{max} and AUC, increased with dose increase from 1 to 30 mg after single dosing. The geometric means of apparent volume of distribution (V_z/F) and apparent oral clearance (CL/F) were approximately 209-268 L and 18.2-23.0 L/h, respectively, across all dose levels. The geometric mean $t_{1/2}$ values were similar across dose levels, with values ranging from 7.06 to 9.37 hours.

Study CCI [REDACTED] (Completed)

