In a phase 2, multi-center, open-label trial to evaluate the safety and efficacy of umbralisib in previously treated NHL patients, a total of 208 patients were enrolled, including 69 MZL, 117 FL, and 22 SLL. MZL patients were refractory to at least one line of anti-CD20, and FL/SLL patients were refractory to at least two lines of therapy, including an anti-CD20. The ORR in FL patients was 45.3% with 5.1% CR and DoR of 11.1 months (range 8.3-15.6 months). The median TTR was 2.8 months (range 2.7 to 2.9). The ORR in MZL patients was 49.3% with 15.9% CR and DoR not yet reached at time of publication. The median TTR was 2.8 months (range 2.7 – 2.9). Safety data revealed serious adverse events in 28.1% of patients, with 24.6% \geq grade 3. The most common \geq grade 3 AEs were neutropenia (11.5%), diarrhea (10.1%) and increased ALT/AST (7.2%). Other AEs of interest included pneumonitis (all grade 1.4%; \geq grade 3 1.0%), and colitis (all grade 1.4%; \geq grade 3 0.5%) (Zinzani 2020).

Overall, approved PI3k- δ inhibitors have demonstrated a modest ORR in the range of 40% to 50% in FL and MZL. However, they demonstrate a low CR rate of 1-16% and mPFS of less than 12 months. While these agents represent a manageable toxicity profile, high rates of diarrhea, colitis, and hepatic toxicity results in a high rate dose reduction and treatment discontinuation, thereby impacting the long term benefit. Therefore, there is room for a more efficacious and tolerable PI3K- δ inhibitor for treatment of NHL (Dreyling 2017, Zinzani 2020, Flimm 2019).

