5.7.11 Electrocardiogram

All electrocardiograms (ECGs) are required to be performed using a 12-lead tracing. ECG measurements will include PR interval, QRS interval, RR interval, QT/QTcF interval, and heart rate.

For dose escalation stage, triplicate ECGs, approximately 2 minutes apart, should be performed at screening, pre-dose, and 2 ± 0.5 and 4 ± 0.5 hours post-dose on Days 1 and 15 of Cycle 1 in order to evaluate concentration-QT relationship with HMPL-689. Single ECG will be conducted at any time on Day 1 of every cycle from Cycle 2 and onwards, and at study completion or early termination. For dose expansion stage, ECGs should be collected according to the schedule and time points in [Appendix 3](#).

Additional ECGs and other cardiac monitoring will be provided as clinically indicated during the study.

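### The ECG analysis set excludes whole patients for dosing events after the Cycle 1 Day 15 ECG, so valid QTc triplicates leave the analysis because of later events

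*Protocol*

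**What the plan says.** Protocol 7.3.5 admits to the ECG evaluation patients who took at least one dose and "have baseline and at least 1 postdose ECG measurement will be evaluable for pharmacodynamic (ECG) evaluation". It then excludes "Patients who had reduced dosage, prolonged dose interruption of >2 days in cycle 1", patients with "any dose interruption within 3 days before Cycle 1 Day 15", and those who were "discontinued from the study prior to the completion of ECG data collection (Cycle 1 Day 15) will be excluded". No cause is required for any item, and exclusion is by patient rather than by time point.

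Protocol 5.7.11 schedules the escalation-stage triplicates at screening, before dosing, and at 2 and 4 "hours post-dose on Days 1 and 15 of Cycle 1 in order to evaluate concentration-QT relationship with HMPL-689". Protocol 7.3.5.1 summarises QTc change at each time point and takes the Day 15 change around the time of peak concentration as primary. Protocol 4.2 defines a cycle as 28 days.

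SAP sections 6.1 to 6.4 define no ECG set. SAP 17.5 names the ECG parameters to be reported and lists the data, with no exclusion rule.

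**The concern.** An analysis set should not depend on what happens after the measurement it is meant to support. Here a patient with clean Day 1 and Day 15 triplicates is removed if dosing is interrupted for more than two days in the second half of the cycle, or if the dose is reduced at some later date. The Day 1 post-dose ECGs are lost as well, although no later event can touch them.

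Later events need not be unrelated to exposure. Protocol 5.4.1 requires dosing to be interrupted after a DLT, and the DLT window runs to Day 28 (4.1.1.3). A DLT on Day 20 whose interruption lasts more than two days would take that patient's earlier ECGs out of the analysis. If such events follow exposure, so does membership of the set. The effect on QTc is a stated secondary objective, and this set feeds its primary analysis.

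**Working it through.** The documents give no size or expected exclusion count for the ECG set, so there is no planned figure to reproduce. Three checks follow.

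**1. Where a gap can fall.** Days after the Day 15 ECG: 28 − 15 = 13. The shortest whole-day interruption above two days is three days. With the first dose on Day 1, it can start on Days 2 to 26, which is 25 possible starts:

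- starts on Days 16 to 26: 11, wholly after the Day 15 ECG
- starts on Days 2 to 9: 8, ending by Day 11 and so outside the separate 3-day clause
- starts on Days 10 to 15: 6, touching Days 12 to 15

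11 + 8 + 6 = 25. These are day counts only.

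**2. What a gap does to the Day 15 level.** The model is one-compartment superposition of once-daily doses. The level just after the Day 15 dose time, relative to uninterrupted dosing, is

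R = Σ(doses taken) 2^(−24(15−d)/h) ÷ Σ(d = 1 to 15) 2^(−24(15−d)/h),

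where h is the half-life in hours. Protocol 2.3 gives single-dose geometric mean half-lives in healthy volunteers that "were similar across dose levels, with values ranging from 7.06 to 9.37 hours". Protocol 4.2 gives an accumulation ratio of about 1 to 2 in patients. With daily dosing a ratio of 2 means 1/(1 − 2^(−24/h)) = 2, so h = 24. That study also dosed twice daily; a ratio of 2 at a 12-hour interval would give h = 12, so 24 h is the cautious choice.

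| Doses missed | h = 7.06 | h = 9.37 | h = 24 |
|---|---|---|---|
| Days 16–18 | 100% | 100% | 100% |
| Days 2–4 | 100.0% | 100.0% | 99.96% |
| Days 6–8 | 100.0% | 100.0% | 99.3% |
| Days 9–11 | 99.99% | 99.92% | 94.5% |
| Days 2–11 | 99.99% | 99.92% | 93.8% |
| Days 12–14 | 90.5% | 83.1% | 56.2% |
| Day 15 dose | 9.5% | 16.9% | 50.0% |

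The last row is 2^(−24/h) to rounding. Late gaps do nothing, and gaps ending by Day 11 do little. Gaps on Days 12 to 14 matter and are covered by the 3-day clause. A gap starting on Day 15 matters most, and the 3-day clause, which looks only at the days before Day 15, misses it.

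**3. Precision.** If a fraction f of a large group is excluded, the 90% confidence interval widens by about 1/√(1−f). For f of 5%, 10%, 20% and 30% that is 1.03, 1.05, 1.12 and 1.20. These fractions are assumptions; the documents give no rate for these exclusions in this study.

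**The case against.** **The end point in the last item might govern every item.** If so, events after Day 15 would not exclude anyone. But the two interruption items carry their own time limits, so the phrase attaches most naturally to leaving the study. If the wider reading is meant, the text should say so, and the loss of Day 1 data would remain.

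**The data are not lost to the report.** This is correct. Protocol 7.3.2 and 7.3.2.5 summarise ECG parameters by dose level for the full analysis set without these exclusions, and the SAP lists all ECG data. The loss is confined to the 7.3.5 analysis, which has no hypothesis test attached.

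**The clause of more than two days might look redundant, so that it could simply be deleted.** The documents do not support that. An interruption starting on Day 15 is caught only by this clause, and without the Day 15 dose the level is about 9 to 17% of the uninterrupted value at the stated half-lives. Nor is recovery after an early gap complete on every assumption: at 24 h, three doses after full washout restore 1 − 2^(−72/24) = 87.5% before the Day 15 dose.

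**Early reductions are rightly excluded.** This also stands. Protocol 5.4.1 does not allow a reduced dose to be raised again, so a reduction in the DLT window before Day 15 still applies on Day 15. Early events that no longer matter are interruptions only.

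**Conclusion.** The point holds as a minor fault in how the set is defined. On the natural reading of 7.3.5, events on Days 16 to 28, and undated reductions later still, remove Day 15 and Day 1 ECGs that they cannot have affected, and nothing in the SAP corrects this. The late-event conclusion needs no pharmacokinetic assumption. The statement about early gaps rests on the one-compartment model and the half-lives used above.

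A reader might infer that the rule biases the mean QTcF change downward by a calculable amount. The documents do not support that. They give no rate for these exclusions in this study and no link between exposure and interruption; the rule also counts missed doses of any cause; and in the DLT window a reduction without a DLT needs sponsor approval. The remark in Protocol 2.4 that class toxicity "results in a high rate dose reduction and treatment discontinuation" concerns the approved inhibitors, not HMPL-689 in Cycle 1. Selection on exposure is possible, but its size and direction cannot be worked out.

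**What to change.** Rewrite the exclusions in Protocol 7.3.5 by time point:

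- **Day 1:** use post-dose ECGs from every patient with a baseline and a Day 1 post-dose ECG.
- **Day 15:** exclude only patients with a dose reduction before the Day 15 ECG, any missed dose or interruption from 3 days before Day 15 up to and including the Day 15 dose, or no Day 15 ECG.
- **Interruptions of more than two days:** limit the clause to those before the Day 15 ECG, or drop it once the Day 15 dose is covered by the item above.
- State that events after the Day 15 ECG never exclude a patient.

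Add this ECG set to SAP section 6, and refer to it in 17.5.

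The cost is one protocol paragraph and one SAP entry. No new data are needed and no dosing rule changes. If the clause is dropped, a few patients with an earlier, largely recovered interruption stay in the Day 15 mean; if it is only limited in time, they stay out.
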